7.1.4 Response Criteria

7.1.4.1 Evaluation of Target Lesions

Complete Response (CR): Disappearance of all target lesions, determined by two separate observations conducted not less than 4 weeks apart. There can be no appearance of new lesions.

Partial Response (PR): At least a 30% decrease in the sum of the longest diameter (LD) of target lesions, taking as reference the baseline sum LD. There can be no appearance of new lesions.

Progressive Disease (PD): At least a 20% increase in the sum of the LD of target lesions, taking as reference the smallest sum LD recorded since the treatment started, or the appearance of one or more new lesions.

Stable Disease (SD): Neither sufficient shrinkage to qualify for PR nor sufficient increase to qualify for PD, taking as reference the smallest sum LD since the treatment started.

7.1.4.2 Evaluation of Non-Target Lesions

Complete Response (CR): Disappearance of all non-target lesions and normalization of tumor marker level.

Incomplete Response/Stable Disease (SD): Persistence of one or more non-target lesion(s) and/or maintenance of tumor marker level above the normal limits.

Progressive Disease (PD): Appearance of one or more new lesions and/or unequivocal progression of existing non-target lesions.

7.1.4.3 Evaluation of Best Overall Response

The best overall response is the best response recorded from the start of the treatment until disease progression/recurrence (taking as reference for progressive disease the smallest measurements recorded since the treatment started). The patient's best response assignment will depend on the achievement of both measurement and confirmation criteria.

| Target Lesions | Non-Target Lesions | New Lesions | Overall Response | Best Response for this Category Also Requires: |
|----------------|--------------------|-------------|------------------|--|
| CR | CR | No | CR | ≥4 wks. confirmation |
| CR | Non-CR/SD | No | PR | ≥4 wks. confirmation |
| PR | Non-PD | No | PR | |
| SD | Non-PD | No | SD | documented at least once ≥4 wks. from baseline |
| PD | Any | Yes or No | PD | no prior SD, PR or CR |
| Any | PD* | Yes or No | PD | |
| Any | Any | Yes | PD | |

* In exceptional circumstances, unequivocal progression in non-target lesions may be accepted as disease progression.

Note: Patients with a global deterioration of health status requiring discontinuation of treatment without objective evidence of disease progression at that time should be reported as “*symptomatic deterioration*”. Every effort should be made to document the objective progression even after discontinuation of treatment.

Note: If subjects respond to treatment and are able to have their disease resected, the patient’s response will be assessed prior to the surgery.

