1.3 Study Design/Schema

Registered subjects will take pazopanib by mouth with a low-fat meal (**containing less than 400 calories and less than 20% fat or 10 grams per meal**) approximately, some sample meals are described in appendix 1) every day in 14 day cycles, for a total of 6 cycles, with a starting dose of 400 mg and adjusted for the next cycle (dose level +1: 600 mg; dose level +2: 800 mg; dose level -1: 200 mg) based on toxicity assessment during or at the end of each cycle. No dose re-escalations are permitted. Imaging will be performed post 12 weeks of treatment.

An interim analysis for safety will be performed after 8 subjects have completed at least 2 cycles (4 weeks) of therapy.

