7.1.2 Disease Parameters

Measurable disease. Measurable lesions are defined as those that can be accurately measured in at least one dimension (longest diameter in the plane of measurement is to be recorded) with a minimum size of:

- 10mm by CT scan (irrespective of scanner type) for studies with a slice thickness of ≤ 5 mm or twice the slice thickness or MRI
- 10mm caliper measurement by clinical exam (lesions which cannot be accurately measured with calipers should be recorded as non-measurable)
- 20mm by chest X-ray (if clearly defined and surrounded by aerated lung)

All tumor measurements must be recorded in millimeters (or decimal fractions of centimeters).

Malignant lymph nodes: To be considered pathologically enlarged and measurable, a lymph node must be ≥ 15 mm in short axis when assessed by CT scan (CT scan slice thickness recommended to be no greater than 5 mm). At baseline and 28 days post therapy, only the short axis will be measured and followed.

Note: Tumor lesions that are situated in a previously irradiated area might or might not be considered measurable, and the conditions under which such lesions should be considered may be defined in the protocol when appropriate.

Non-measurable disease. All other lesions (or sites of disease), including small lesions (longest diameter <20 mm with conventional techniques or <10 mm using CT scan), are considered non-measurable disease. Bone lesions, leptomeningeal disease, ascites, pleural/pericardial effusions, lymphangitis cutis/pulmonis, inflammatory breast disease, abdominal masses (not followed by CT or MRI), and cystic lesions are all non-measurable.

Target lesions. All measurable lesions up to a maximum of 2 lesions per organ and 5 lesions in total should be identified as **target lesions** and recorded and measured at baseline. Target lesions should be selected on the basis of their size (lesions with the longest diameter), be representative of all involved organ, but in addition should be those that lend themselves to reproducible repeated measurements.

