11.0 STATISTICAL CONSIDERATIONS

11.1 Study Design/Study Endpoints and Data Assessment Plan

Pazopanib with a low fat diet is a pilot study with a primary endpoint of feasibility and safety.

The primary outcome will be a description of toxicity and feasibility with the following endpoints: any hematologic toxicity of grade 4 or non-hematologic toxicities of grades 3 and 4 (excluding alopecia, and also excluding nausea and vomiting if the symptoms were manageable with standard care or antiemetic therapy); frequency and proportion of toxicities of all grades according to the CTCAE version 4.0 criteria; the frequency of dose reductions; the duration of treatment and the mean (or median) total dose taken. Each endpoint will include a 95% confidence around the reported statistic. Examples of exact confidence interval ranges with a sample size of 16 are presented in table 3.

Table 5:

| Frequency | Proportion | 95% Confidence Interval |
|-----------|------------|-------------------------|
| 1 | 6.25% | 0.2%, 30.2% |
| 2 | 12.5% | 1.6%, 38.4% |
| 3 | 18.75% | 4.1%, 45.7% |
| 6 | 37.5% | 15.2%, 64.5% |
| 8 | 50% | 24.7%, 75.4% |

The secondary objectives include overall response proportion by RECIST 1.1 including complete response and partial response at 12 weeks after start of pazopanib therapy start (CT chest, abdomen and pelvis). Each response proportion will be expressed with 95% exact binomial confidence intervals.

The pharmacokinetic data (Cmax in units of ng/mL and the trough concentration in units of micro g/mL) will be reported in context of known PK data of pazopanib administered in the fasting state⁷ and described in the context of the toxicity data.

An interim safety analysis will be conducted after 8 patients have been treated for 2 cycles on pazopanib with a low fat meal. If greater than 5 patients of the 8 experience hematologic toxicity of grade 4 or non-hematologic toxicities of grades 3 or 4 (excluding alopecia, and also excluding nausea and vomiting if the symptoms were manageable with standard care or antiemetic therapy), the study will be pause. Further study may be continued with an amendment to decrease the starting dose to 200 mg PO daily with low fat meal subject to PRC review/approval and IRB review/approval.

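### Complete response needs a second observation at least 4 weeks later, but only one post-baseline scan is scheduled, so no CR can be assigned from scheduled data

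*Combined protocol and SAP*

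**What the plan says.** **Response rule.** Section 7.1.4.1 defines target-lesion CR as "Disappearance of all target lesions, determined by two separate observations conducted not less than 4 weeks apart". It defines PR as "At least a 30% decrease in the sum of the longest diameter (LD) of target lesions, taking as reference the baseline sum LD", with no upper limit on shrinkage and no second observation. Section 7.1.4.3 adds: "The patient's best response assignment will depend on the achievement of both measurement and confirmation criteria". Two rows of its table, read in the order target, non-target, new lesions, overall response, further requirement, carry a confirmation condition: "CR | CR | No | CR | ≥4 wks. confirmation" and "CR | Non-CR/SD | No | PR | ≥4 wks. confirmation". The row for target PR with non-target lesions not progressing gives overall PR, and its requirement cell is empty.

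**Schedule.** Section 1.3 says: "Imaging will be performed post 12 weeks of treatment". Section 6.3.3 places CT at the EOT visit, and the calendar in 6.4 marks body CT at screening and EOT only. Section 6.3.4 lists examination, vital signs, laboratory tests and a toxicity check 28 days (± 7) after EOT, without imaging. Under 5.6, follow-up ends 28 days after removal from treatment, except for patients removed for unacceptable adverse events.

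**Endpoint.** Section 11.1 describes the response endpoint as including "complete response and partial response at 12 weeks after start of pazopanib therapy", with exact 95% intervals, and does not mention confirmation.

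**A stray reference.** Section 7.1.2 says of lymph nodes: "At baseline and 28 days post therapy, only the short axis will be measured and followed". No scan is scheduled at that time.

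**The concern.** The rule for CR calls for data that the schedule does not collect. If the analysis follows section 7 literally, the CR count is zero whatever the drug does, and a reader of the results would take that as a finding about the regimen.

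The plan also does not say what becomes of a patient whose target lesions have all gone on the only scan. That choice would be made after the scan has been read, in an open-label single-centre study where one patient is a visible share of the response proportion.

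**Working it through.** **1. The plan's own figures.** Section 11.1 tabulates exact intervals for n = 16. The Clopper-Pearson limits for x responders are the 2.5% quantile of Beta(x, n − x + 1) and the 97.5% quantile of Beta(x + 1, n − x).

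| x/16 | Plan, % | Recomputed, % |
|---|---|---|
| 1 | 0.2, 30.2 | 0.16, 30.23 |
| 2 | 1.6, 38.4 | 1.55, 38.35 |
| 3 | 4.1, 45.7 | 4.05, 45.65 |
| 6 | 15.2, 64.5 | 15.20, 64.57 |
| 8 | 24.7, 75.4 | 24.65, 75.35 |

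All agree to within 0.1 point, so the same method is used below.

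**2. Observations needed against observations scheduled.**
- Needed for either target-CR row: 2, at least 28 days apart (7.1.4.1, 7.1.4.3).
- Scheduled body scans after baseline: 1 (1.3, 6.3.3, 6.4).
- Shortfall: 2 − 1 = 1.

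A scan added at the existing post-EOT visit would not reliably close the gap. The window of 28 ± 7 days runs from 21 to 35 days after EOT, so it can fall short of 4 weeks.

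**3. Consequence for CR.** The reported count would be 0/16. With x = 0 the exact upper limit is 1 − 0.025^(1/16) = 1 − 0.794 = 20.6%. An interval of 0 to 20.6% would be printed for a quantity that the schedule had fixed at zero.

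**4. Consequence for CR + PR.** Take a patient whose target lesions are absent at EOT, with no new lesions and no non-target progression.
- *Reading A.* Target CR needs two observations, so one observation is not yet target CR. A 100% decrease is at least 30%, so the patient meets target PR. The target-PR row gives overall PR without confirmation, and ORR is unchanged.
- *Reading B.* Disappearance places the patient in a target-CR row. Both such rows need confirmation that is not scheduled, and the table gives no fallback, so no response is assigned.

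Neither reading is comfortable. Under A, the confirmation cell in the row for target CR with non-target non-CR does no work, because those patients are already PR on one scan. Under B, complete disappearance faces a stricter test than a 30% decrease.

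**5. Size under reading B.** One patient is 1/16 = 6.25 points. For illustration, assume 5 of 16 respond, near the 30% quoted in section 1.1, and one of the five has complete target disappearance.
- Counted: 5/16 = 31.3% (11.0 to 58.7).
- Not counted: 4/16 = 25.0% (7.3 to 52.4).

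**6. Chance that the case arises.** The documents give no CR rate. For an assumed rate p, the chance of at least one such patient in 16 is 1 − (1 − p)^16.

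| p | 1% | 2% | 3% | 5% | 10% |
|---|---|---|---|---|---|
| Chance | 15% | 28% | 39% | 56% | 81% |

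**The case against.** The strongest reply is that section 11.1 already defines a time-point response at 12 weeks, says nothing of confirmation, and fits the single scan. On that view the confirmation wording in section 7 has no bearing on the analysis. This is a fair reading, and the fix below adopts it. But 11.1 cites RECIST 1.1 without setting section 7 aside, and section 7 is where the protocol says how response is to be assigned. The two sections conflict until one of them is changed.

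A reader might go further and infer that the deepest responders have no valid response class and therefore drop out of ORR. The documents do not establish that. The PR definition has no ceiling and the ordinary PR row needs no confirmation, so reading A keeps these patients in the numerator. The lower ORR in step 5 follows only from reading B, with an assumed number of affected patients.

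It can also be said that later scans are not forbidden and that best response in 7.1.4.3 runs to progression rather than to EOT. That is true. However, no rule says such scans may be used, and under 5.4 patients may by then have moved to another therapy, so a later scan might not reflect this regimen.

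Finally, no test, stopping rule or decision in the plan uses ORR, and the sample is a convenience sample of 16. That limits the severity. It does not remove the contradiction.

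**Conclusion.** Wrong as written, with modest severity. From scheduled scans no CR can be assigned, and neither can PR by the row for target CR with non-target non-CR. The CR proportion promised in 11.1 is therefore 0% by construction. This rests on the schedule and the rule alone and needs no assumed rate.

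For ORR the defect is an ambiguity, not a demonstrated loss: no change under reading A, and 6.25 points per affected patient under reading B. That figure assumes all 16 patients are in the denominator; the evaluability rule in 7.1.1 could make it smaller, and each patient's share correspondingly larger. Even on reading B, the shift for one patient is small beside an exact interval about 48 points wide (58.7 − 11.0 = 47.7). The primary safety and feasibility endpoints are not affected.

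**What to change.** Align section 7 with section 11.1:

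1. State that response is the unconfirmed RECIST 1.1 CR or PR on the single EOT scan at about 12 weeks.
2. In 7.1.4.1, delete the clause that requires two observations at least 4 weeks apart for CR.
3. In 7.1.4.3, clear the 4-week confirmation cells in both target-CR rows, and amend the sentence that makes best response depend on confirmation. If that sentence stays, the contradiction stays.
4. Reconcile the nodal measurement at 28 days after therapy in 7.1.2 with the imaging calendar.

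This is a wording amendment with no extra scan, to be made before the EOT scans are read. Its cost is that ORR must be labelled unconfirmed, which limits comparison with confirmed response rates.

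The alternative is to keep confirmation and schedule a second scan at least 28 days after EOT, with a window that cannot open earlier. That costs an added scan per responder, and the scan would come after protocol therapy has ended. The plan would still need a rule for an unconfirmed disappearance. For a descriptive pilot the wording change is the more proportionate repair.

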7.1.5 Duration of Response

Duration of overall response: The duration of overall response is measured from the time measurement criteria are met for CR or PR (whichever is first recorded) until the first date that recurrent or progressive disease is objectively documented (taking as reference for progressive disease the smallest measurements recorded since the treatment started).

The duration of overall CR is measured from the time measurement criteria are first met for CR until the first date that recurrent disease is objectively documented.

Duration of stable disease: Stable disease is measured from the start of the treatment until the criteria for progression are met, taking as reference the smallest measurements recorded since the treatment started.

7.1.6 Progression-Free Survival

Progression-free survival (PFS) is defined as the duration of time from registration to time of progression.

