In a subsequent non-inferiority trial, pazopanib was compared to sunitinib in therapy of clear cell metastatic renal-cell carcinoma, in 1110 patients who were randomized in a 1:1 manner to receive continuous pazopanib (800 mg once daily on an empty stomach; 557 patients) or sunitinib in 6-week cycles (50 mg once daily for 4 weeks, followed by 2 weeks without treatment; 553 patients)². The primary end point was progression-free survival as assessed by independent review, and the study was powered to show non-inferiority of pazopanib versus sunitinib. Secondary end points included overall survival, safety, and quality of life. Pazopanib was shown to be non-inferior to sunitinib with respect to progression-free survival (hazard ratio for progression of disease or death from any cause, 1.05; 95% confidence interval [CI], 0.90 to 1.22), meeting the predefined non-inferiority margin (upper bound of the 95% confidence interval, <1.25). Overall survival was also similar (hazard ratio for death with pazopanib, 0.91; 95% CI, 0.76 to 1.08). Patients treated with sunitinib, as compared with those treated with pazopanib, had a higher incidence of fatigue (63% vs. 55%), hand-foot syndrome (50% vs. 29%), and thrombocytopenia (78% vs. 41%). Patients treated with pazopanib had a higher incidence of increased levels of alanine aminotransferase (60%, vs. 43% with sunitinib). The mean change from baseline in 11 of 14 health-related quality-of-life domains, particularly those related to fatigue or soreness in the mouth, throat, hands, or feet, during the first 6 months of treatment favored pazopanib ($P < 0.05$ for all 11 comparisons)².

Pazopanib has since become one of the standard first line therapies in metastatic RCC³. If other agents are chosen in the first line setting, pazopanib is often used in subsequent lines of therapy.

Pazopanib Dosing

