2.3 Endpoints

2.4 Primary Endpoint:

- 2.4.1 To assess the frequency of grade 3 or 4 adverse events associated with pazopanib administered with a low fat meal by CTCAE ver 4.0.

2.5 Secondary endpoints:

- 2.5.1 To estimate the overall response proportion to pazopanib administered with a low fat meal by RECIST 1.1 criteria.
- 2.5.2 To explore Cmax in subjects treated with pazopanib administered with a low fat meal and its potential correlation with toxicity as assessed by CTCAE ver 4.0

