5.4 Duration of Therapy

In the absence of treatment delays due to adverse events, treatment may continue until one of the following criteria apply:

- Disease progression as defined in Section 7.0
- Inter-current illness that prevents further administration of treatment as deemed appropriate by treating physician.
- Unacceptable adverse event(s) as defined in Section 8.0

- Patient voluntarily withdraws from treatment OR changes in the patient's condition render the patient unacceptable for further treatment in the judgment of the investigator.
- Completion of therapy with pazopanib with low fat meal for 12 weeks. Patients could then go onto standard therapies, including pazopanib given without food/low fat meal.

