11.2 Sample Size and Accrual

A sample size of 16 patients with metastatic renal cell carcinoma will be enrolled over a 12 month period with an interim analysis for safety after 8 patients have completed 2 cycles. As a pilot study, this sample size is a convenience sample and sufficient to determine the feasibility of administering pazopanib with a low-fat meal in advanced renal cell carcinoma, the associated toxicity profile and preliminary efficacy measures such as ORR, PFS or overall survival.

Based on data from this pilot study, a larger follow-up study may be warranted to definitively address the cost savings of administering pazopanib with low fat meal and the efficacy of the drug when given with low fat meal.

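### Section 7.1.6 defines PFS by progression alone, which is time to progression, so PFS would be overstated if a patient died without documented progression

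*Combined protocol and SAP*

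**What the plan says.** The only definition of PFS is in section 7.1.6: "Progression-free survival (PFS) is defined as the duration of time from registration to time of progression". Progression is defined in section 7.1.4. For target lesions it means "At least a 20% increase in the sum of the LD of target lesions, taking as reference the smallest sum LD recorded since the treatment" began, or new lesions; for non-target lesions it means new lesions or unequivocal worsening. Death is not part of either criterion or of the best-response table in 7.1.4.3.

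Section 11.2 refers to "preliminary efficacy measures such as ORR, PFS or overall survival" when it explains what 16 patients can show. Sections 2.4 and 2.5 do not list PFS. The only efficacy endpoint there is "To estimate the overall response proportion to pazopanib administered with a low fat meal by RECIST 1.1 criteria". Section 11.1 gives no survival method and no censoring rule.

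On timing, section 1.3 says "Imaging will be performed post 12 weeks of treatment", and the study calendar in 6.4 shows no earlier on-study scan. Section 5.4 ends protocol treatment on "Completion of therapy with pazopanib with low fat meal for 12 weeks", unless it stops sooner. Section 5.6 follows patients for a further 28 days or to death.

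In section 1.1, the PFS result of the cited non-inferiority trial against sunitinib is described as a "hazard ratio for progression of disease or death from any cause".

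**The concern.** An endpoint called progression-free survival normally counts death as a failure. Under 7.1.6 a patient who dies without documented progression has no event. The plan does not say whether that patient is then censored at death, counted as event-free or dropped, so whoever runs the analysis has to choose. Censoring or counting as event-free pushes the estimate up whenever such a death occurs, because a patient with a poor outcome is not counted as a failure.

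The schedule makes the situation possible. With one scheduled scan after 12 weeks, a patient who dies earlier may have had no imaging that could show progression. Section 11.2 also foresees a larger follow-up study based on these data, partly on efficacy, so any PFS figure reported from the pilot may be read by people planning that study. They would take the label at face value.

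**Working it through.** The documents give no PFS figure, event count, power or analysis method, so there is no planned number to reproduce. The check has three steps.

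**1. Does any other text repair the definition?** The progression criteria in 7.1.4 cover lesion growth and new lesions only. Section 7.1.4.3 labels decline without objective progression as symptomatic deterioration, not as progression. Sections 2.5, 11.1 and 11.2 add no event or censoring rule. Section 5.6 follows patients to death within its window but does not tie death to PFS. Nothing repairs it.

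**2. What can one death do in 16 patients?** The number of patients (16) comes from 11.2. The events are assumed: 3 progressions, and 1 death that precedes all of them, with the other patients followed to the end.

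| Handling of the death | Calculation | Event-free |
|---|---|---|
| Counted as an event | 1 − (3 + 1)/16 = 12/16 | 75.0% |
| Censored before any progression | (14/15) × (13/14) × (12/13) = 12/15 | 80.0% |
| Treated as event-free | 1 − 3/16 = 13/16 | 81.3% |

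The shift is 80.0 − 75.0 = 5.0 points or 81.25 − 75.0 = 6.25 points, depending on a choice that the plan leaves open. With no such death, all three rows give 13/16 = 81.3% and the difference is zero.

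**3. How likely is it, and how large on average?** This step is illustrative. From the documents: median PFS of 9.2 months overall, 7.4 months cytokine-pretreated and 11.1 months treatment-naive (placebo-controlled trial, section 1.1), and an observation window of 12 weeks plus 28 days = 16 weeks. Assumed, not in the documents: constant hazards, those medians taken as progression or death, and a share f of first events that are deaths without progression, from 5% to 30%.

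- Total hazard: λ = ln 2 / median. For 9.2 months, λ = 0.0753 per month.
- Time: 16 weeks = 16 × 7 / 30.4375 = 3.68 months.
- With deaths counted: exp(−λt) = exp(−0.277) = 75.8%.
- With deaths censored: exp(−λ(1 − f)t) = 76.8% for f = 5% and 82.4% for f = 30%.
- Overstatement: 1.1 to 6.6 points.
- Expected deaths without progression: 16 × (1 − 0.758) × f = 0.19 to 1.16.
- Chance of at least one: 1 − (1 − 0.242f)^16 = 18% to 70%.

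Across the three medians and both 12 and 16 weeks, the overstatement runs from 0.7 to 7.7 points, the expected number of such deaths from 0.13 to 1.40, and the chance of at least one from 12% to 77%.

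**The case against.** The best defence is that nothing planned depends on this. PFS is absent from 2.4, 2.5 and the analyses in 11.1. Section 11.2 names it only as an example, in a paragraph that also says "As a pilot study, this sample size is a convenience sample". No sample size, stopping rule or decision uses it. That is correct and keeps the impact small. It would be too strong to read 11.2 as a commitment to report PFS. It does not make the definition right: 7.1.6 states a rule, and following it gives a different quantity from the one named.

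A reader might infer that anyone who dies before the 12-week scan cannot have progressed under this definition. The documents do not support that. Section 5.4 stops treatment for progression at any time, 7.1.1 expects some objective progression before the end of cycle 1, 7.1.3 allows clinical measurement of lesions that cannot be imaged, and 7.1.4.3 asks for every effort to document progression after patients stop for deterioration. Only deaths with no documented progression are affected.

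A reader might also infer that the definition is what keeps the result from being compared with the background PFS figures. That goes too far. The wording that includes death belongs to a hazard ratio against sunitinib, and this pilot has no control group. The quoted medians come from the other, placebo-controlled trial, and the protocol does not state that trial's PFS event. Observation of about 3.7 months is unlikely to reach medians of 7.4 to 11.1 months under either definition. The mismatch with the wording in 1.1 is worth noting, but correcting 7.1.6 would not by itself make the figures comparable.

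Finally, 5 or 6 points is small beside the sampling error: the exact 95% interval for 12/16 is 47.6% to 92.7%. True, but any bias from leaving deaths out of the event count runs in the favourable direction, and it is avoidable.

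**Conclusion.** Wrong as written, with minor impact. Section 7.1.6 defines time to progression and labels it PFS, and no other section adds death or a censoring rule. It does not follow that PFS will be overstated: that needs at least one death without documented progression, and otherwise the difference is zero. In the worked example, one such death among 16 patients raises the event-free figure by 5.0 to 6.25 points. The example rests on assumed events and on how the death is handled; the model range rests on constant hazards and an assumed death share. The primary safety results and the response proportion do not use this definition and are unaffected.

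**What to change.** Replace the sentence in 7.1.6 with: PFS is the time from registration to first documented progression or death from any cause, whichever is first; patients alive and progression-free are censored at their last tumour assessment.

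Alternatively, keep the present event, rename the measure time to progression in 7.1.6 and 11.2, and state how deaths without progression are handled.

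The first option costs one sentence and no new data collection, because section 5.6 already follows patients to death or 28 days after treatment. Its downside is that the reported PFS may be slightly less favourable. The second option costs a few words in two sections and gives up a measure that includes death.
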